## **Absence of cirrhosis is defined as any one of the following:**

- a. Liver biopsy performed within 24 months of Day 1 of this study showing absence of cirrhosis
- b. Fibroscan performed within 12 months of Day 1 of this study with a result of  $\leq 12.5$  kPa [29]\*
- c. A FibroSure (Fibrotest) score of  $\leq 0.48$  and AST to Platelet Ratio Index (APRI) of  $\leq 1$  during Screening

Fibroscan cut-off of 12.5 kPa has a positive predictive value of 90% and a sensitivity of 95% for  $\geq F3$ . Based on box and whisker plot of interquartile distribution  $>12.5$  kPa will exclude the majority of subjects with metavir F3 fibrosis. In the absence of a definitive diagnosis of presence or absence of

# Proprietary Information of MD Anderson

Protocol # 2016-0251

Date: February 24, 2020

40

cirrhosis by the above criteria, a liver biopsy is required. Liver biopsy results supersede the results obtained by Fibroscan or Fibrosure.

9. Have a predicted life expectancy of greater than 3 months.
10. Have measurable disease based on RECIST 1.1 as confirmed by the blinded M.D. Anderson radiology. Target lesions situated in a previously irradiated area are considered measurable if progression has been demonstrated in such lesions.

Note: the same image acquisition and processing parameters should be used throughout the study for a given subject..

11. Have a performance status of 0 or 1 using the ECOG Performance Scale within 7 days of first dose of study drug.
12. Have documented objective radiographic progression after stopping treatment with sorafenib or else intolerance to sorafenib. Intolerance to sorafenib is defined as: NCI CTCAE version 4.0 (Section 12.4) Grade  $\geq 2$  drug-related AE(s) which both a) persisted in spite of comprehensive supportive therapy according to institutional standards and b) persisted or recurred after sorafenib treatment interruption of at least 7 days and dose reduction by one dose level. Patients treated on sorafenib as the last treatment may start pembrolizumab at least 14 days after the last dose of sorafenib.
13. For Arm B Subjects with chronic active infection by HCV who are untreated or treated are allowed on study
14. Subjects with a past or resolved hepatitis B virus (HBV) infection, defined as having a negative HBsAg test and a positive total hepatitis B core antibody (HBcAb) test and negative HBV DNA test at screening, are eligible for the study.
15. Female subjects of childbearing potential must have a negative urine or serum pregnancy test within 72 hours prior to receiving the first dose of trial medication. If the urine test is positive or cannot be confirmed as negative, a serum pregnancy test will be required.
16. Male subjects of childbearing potential must agree to use an adequate method of contraception as outlined in Section 5.6.3 - Contraception, starting with the first dose of trial therapy through 120 days (Arm A) or 180 days (Arm b) after the last dose of trial therapy.

Note: Abstinence is acceptable if this is the usual lifestyle and preferred contraception for the subject.

17. Be willing to use an adequate method of contraception for the course of the study through 120 days (Arm A) or 180 days (Arm B) after the last dose of study medication (male and female subjects of childbearing potential [Section 5.6.3]). Acceptable methods of contraception are as follows:

Single method (one of the following is acceptable):

- a. intrauterine device (IUD)
- b. vasectomy of a female subject's male partner

# Proprietary Information of MD Anderson

Protocol # 2016-0251

Date: February 24, 2020

41

- c. contraceptive rod implanted into the skin

Combination method (requires use of 2 of the following):

- d. diaphragm with spermicide (cannot be used in conjunction with cervical cap/spermicide)
- e. cervical cap with spermicide (nulliparous women only)
- f. contraceptive sponge (nulliparous women only)
- g. male condom or female condom (cannot be used together)
- h. hormonal contraceptive: oral contraceptive pill (estrogen/ progestin pill or progestin- only pill), contraceptive skin patch, vaginal contraceptive ring, or subcutaneous contraceptive injection

Note: Abstinence (relative to heterosexual activity) can be used as the sole method of contraception if it is consistently employed as the subject's preferred and usual lifestyle and if considered acceptable by local regulatory agencies and Institutional Review Boards (IRBs)/Ethics Review Committees (ERCs). Periodic abstinence (e.g., calendar, ovulation, sympto-thermal, post-ovulation methods, etc.) and withdrawal are not acceptable methods of contraception.

If a contraceptive method listed above is restricted by local regulations/guidelines, then it does not qualify as an acceptable method of contraception for subjects participating at sites in this country/region.

18. Subjects in Arm B treated with RBV must agree to double barrier birth control from Day 1 to 6 months following last dose of study therapy or they are excluded from this trial.

19. Have adequate organ function as defined in [Table 2](#). Specimens must be collected within 7 days prior to the start of trial treatment.

Table 2 Adequate Organ Function Laboratory Tests

System	Laboratory Value	
Hematological		
Absolute neutrophil count	$\geq 1500/\mu\text{L}$	
Platelets	$\geq 100,000/\mu\text{L}$	
Hemoglobin	$\geq 9.0 \text{ g/dL}$ or $\geq 5.6 \text{ mmol/L}^a$	
Renal		
Creatinine	OR $\leq 1.5 \times \text{ULN}$ OR Measured or calculated b creatinine clearance (GFR can also be used in place of creatinine or CrCl)	$\geq 30 \text{ mL/min}$ for subject with creatinine levels $>1.5 \times \text{institutional ULN}$
Hepatic		
Total bilirubin	$\leq 1.5 \times \text{ULN}$ OR direct bilirubin $\leq \text{ULN}$ for subjects with total bilirubin levels $>1.5 \times \text{ULN}$	
AST (SGOT) and ALT (SGPT)	$\leq 2.5 \times \text{ULN}$ ( $\leq 5 \times \text{ULN}$ for subjects with liver metastases)	
Coagulation		

# Proprietary Information of MD Anderson

Protocol # 2016-0251

Date: February 24, 2020

42

System	Laboratory Value
INR or PT aPTT	$\leq 1.5 \times \text{ULN}$ unless subject is receiving anticoagulant therapy as long as PT or aPTT is within therapeutic range of intended use of anticoagulants

Abbreviations: ALT = alanine aminotransferase; aPTT = activated partial thromboplastin time; AST = aspartate aminotransferase; EPO = erythropoietin; GFR = glomerular filtration rate; INR = international normalized ratio; PT = prothrombin time; PTT = partial thromboplastin time; SGOT = serum glutamic oxaloacetic transaminase; SGPT = serum glutamic pyruvic transaminase; ULN = upper limit of normal.

## 5.1.3 Subject Exclusion Criteria

1. Is currently participating in or has participated in a trial of an investigational agent or has used an investigational device within 4 weeks prior to the first dose of trial treatment.

*Note: Subjects must have recovered from all AEs due to previously therapies to  $\leq$ Grade 1 or baseline. Subjects with  $\leq$ Grade 2 neuropathy may be eligible Note: Subjects who have entered the follow-up phase of an investigational trial may participate as long as it has been 4 weeks after the last dose of the previous investigational agent.*

*Note: Subjects who have entered the follow-up phase of an investigational trial may participate as long as it has been 4 weeks after the last dose of the previous investigational agent.*

2. Has had esophageal or gastric variceal bleeding within the last 6 months. All subjects will be screened for esophageal varices, unless such screening has been performed in the past 12 months before first dose of treatment. If varices are present, they should be treated according to institutional standards before starting study treatment.
3. Subjects with alanine aminotransferase (ALT)  $>5 \times \text{ULN}$  at Day 1 are not eligible for enrollment.
4. Subjects with Total Bilirubin (Tbil)  $>2.0 \text{ mg/dL}$  at Day 1 are not eligible for enrollment
5. Subjects with clinically apparent ascites or encephalopathy, or untreated varices are not eligible for enrollment. Subjects with Child-Pugh class B and C liver disease are also ineligible.
6. Portal vein invasion at the main portal branch (Vp4), inferior vena cava, or cardiac involvement of HCC based on imaging.
7. Has had encephalopathy in the last 6 months. Subjects on rifaximin or lactulose to control their encephalopathy are not allowed.
8. Had a solid organ or hematologic transplant.
9. Had prior systemic therapy for HCC other than sorafenib and/or regorafenib, or intercurrent local therapy to the liver tumor between sorafenib and/or regorafenib and study drug.

# Proprietary Information of MD Anderson

Protocol # 2016-0251

Date: February 24, 2020

43

10. For Arm B is taking or plans to take any of the prohibited medications listed in Section 5 of this protocol or taking herbal supplements, including but not limited to St. John's Wort (*Hypericum perforatum*) within 2 weeks of Day 1.
11. Has evidence of history of chronic active hepatitis not caused by HCV, including but not limited to untreated active HBV (see criteria below under criterion 27), drug-induced hepatitis that is not resolved clinically, and autoimmune hepatitis.
12. Has an active autoimmune disease that has required systemic treatment in past 2 years (ie, with use of disease modifying agents, corticosteroids or immunosuppressive drugs). Replacement therapy (eg, thyroxine, insulin, or physiologic corticosteroid replacement therapy for adrenal or pituitary insufficiency) is not considered a form of systemic treatment and is allowed.
13. Has a diagnosis of immunodeficiency or is receiving chronic systemic steroid therapy (in dosing exceeding 10 mg daily of prednisone equivalent) or any other form of immunosuppressive therapy within 7 days prior the first dose of trial drug.
14. Has received locoregional therapy to liver (TACE, TAE, radiation, radioembolization, or ablation) or surgery to liver or other site within 6 weeks prior to the first dose of study drug. Minor surgery must have occurred at least 7 days prior to the first dose of study treatment (Cycle 1, Day 1). Subjects must have recovered adequately (i.e., Grade  $\leq 1$  or baseline) from the toxicity and/or complications from any intervention prior to starting therapy.
15. Has a known history of an additional malignancy, except if the participant has undergone potentially curative therapy with no evidence of that disease recurrence for 5 years since initiation of that therapy.
  - a. Note: *The time requirement does not apply to participants who underwent successful definitive resection of basal cell carcinoma of the skin, superficial bladder cancer, squamous cell carcinoma of the skin, in situ cervical cancer, in situ breast cancer, or other in situ cancers.*
16. Has radiographically detectable (even if asymptomatic and/or previously treated) central nervous system (CNS) metastases and/or carcinomatous meningitis as assessed by local site investigator.
17. Has a history of (non-infectious) pneumonitis that required treatment with steroids or has current pneumonitis.
18. Has an active infection requiring systemic therapy.
19. Has a history or current evidence of any condition, therapy, or laboratory abnormality that might confound the results of the trial, interfere with the subject's participation for the full duration of the trial, or is not in the best interest of the subject to participate, in the opinion of the treating investigator, including dialysis.
20. Has known psychiatric or substance abuse disorders that would interfere with cooperation with the requirements of the trial.

# Proprietary Information of MD Anderson

Protocol # 2016-0251

Date: February 24, 2020

44

21. Is pregnant or breastfeeding, or expecting to conceive or father children within the projected duration of the trial, starting with the screening visit through 120 days after the last dose of trial treatment.
22. Has received prior therapy with an anti-PD-1, anti-PD-L1, or anti-PD-L2 agent or with an agent directed to another stimulatory or co-inhibitory T cell receptor (eg, CTLA-4, OX-40, CD137)..
23. Has severe hypersensitivity ( $\geq$ Grade 3) to pembrolizumab and/or any of its excipients.
24. Has a known history of human immunodeficiency virus (HIV) infection. No HIV testing is required unless mandated by local health authority.
25. Has a known history of active tuberculosis (TB; *Bacillus tuberculosis*).
26. Has received a live vaccine within 30 days prior to the first dose of trial drug. Examples of live vaccines include, but are not limited to, the following: measles, mumps, rubella, varicella/zoster (chicken pox), yellow fever, rabies, *Bacillus Calmette–Guérin* (BCG), and typhoid vaccine. Seasonal influenza vaccines for injection are generally killed virus vaccines and are allowed; however, intranasal influenza vaccines (eg, FluMist®) are live attenuated vaccines and are not allowed.
27. Has untreated active HBV.

Note: Antiviral therapy for HBV must be given for at least 3 months prior to first dose of study drug, and HBV viral load must be less than 100 IU/mL prior to first dose of study drug. Those on active HBV therapy with viral loads under 100 IU/mL should stay on the same therapy throughout study treatment. HBsAg, HBsAb, anti-HBe, anti-HBc and HBV DNA must be measured at baseline and during the study. Those subjects who are anti-HBc (+) and negative for HBsAg and HBV DNA do not require HBV prophylaxis, but need monitoring with HBsAg, HBsAb, anti-HBe, anti-HBc, and HBV DNA

28. HCV-positive subjects received a prior NS5A-containing regimen.
29. Has received a live vaccine within 30 days of planned start of study therapy (Cycle 1, Day 1). Note: The killed virus vaccines used for seasonal influenza vaccines for injection are allowed; however intranasal influenza vaccines (e.g., FluMist®) are live attenuated vaccines and are not allowed.
30. Subjects with a history of significant or unstable cardiac disease are excluded due to the hemolytic anemia associated with RBV. Subjects with proven coronary artery disease or angina.
31. For Arm B subjects with HCV GT1a and have resistance polymorphisms are excluded if they have a CrCl of less than 50 mL/min.
32. Has received prior first-line therapy within 14 days of first dose of study medication.
33. Has a history or current evidence of any condition, therapy, or laboratory abnormality that might confound the results of the trial, interfere with the subject's participation for

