### 4.3.3.3 Ribavirin Dose and Duration

The dose and duration of RBV with Zepatier for HCV GT1a: treatment-naïve with baseline NS5A polymorphisms was established in the C-Worthy trial (57,58). See Zepatier prescribing information. For patients with a creatinine clearance (CrCl) greater than 50 mL per minute, the recommended dosage of RBV is weight-based (less than 66 kg = 800 mg per day, 66 to 80 kg = 1000 mg per day, 81 to 105 kg = 1200 mg per day, greater than 105 kg = 1400 mg per day) administered in two divided doses with food. For patients with CrCl less than or equal to 50 mL per minute, including patients receiving hemodialysis, refer to the RBV tablet.

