## 5.2 Trial Treatments

The treatment to be used in this trial are outlined in Table 3, Table 4, and Table 5. Please see prescribing information for Zepatier and RBV.

Table 3 Trial Treatments

Drug	Dose/Potency	Dose Frequency	Route of Administration	Regimen/Treatment Period	Use
Pembrolizumab	200 mg	Q3W	IV infusion	Day 1 of each 3-week cycle	Experimental
Zepatier	Tablet: 50 mg elbasvir and 100 mg grazoprevir	qday	PO	Daily See Table 4	Experimental
RBV	Capsule: 200 mg See Table 5	qday	PO	Daily	Experimental

Abbreviations: IV = intravenous; PO = oral; Q3W = every 3 weeks; qday = once daily; RBV = ribavirin.

The duration of Zepatier is dependent upon HCV GTs and presence or absence of resistance polymorphisms. Please see Table 4.

Table 4 Zepatier Trial Treatment Duration With or Without Cirrhosis

Patient Population	Treatment	Duration
GT1a: treatment-naïve without baseline NS5A polymorphisms 	Zepatier	12 weeks
GT1a: Treatment-naïve or PegIFN/RBV-experienced  or with baseline NS5A polymorphisms 	Zepatier + RBV 	16 weeks
GT1b: Treatment-naïve or PegIFN/RBV-experienced 	Zepatier	12 weeks
GT1a  or GT1b: PegIFN/RBV/PI-experienced 	Zepatier + RBV 	12 weeks
GT4: Treatment-Naïve	Zepatier	12 weeks
GT4: PegIFN/RBV-experienced 	Zepatier + RBV 	16 weeks

Abbreviations: GT = genotype; NS5A = non-structural protein 5A; PegIFN = pegylated interferon; RBV = ribavirin.

1. Patients who have failed treatment with PegIFN + RBV.
2. NS5A RAVs at amino acid positions 28, 30, 31, or 93. See Section 2.1 Testing prior to the initiation of therapy, subsection NS5A resistance testing in HCV GT1a-infected patients.
3. For patients with CrCl >50 mL per minute, the recommended dosage of RBV is weight-based (<66 kg = 800 mg per day, 66 to 80 kg = 1000 mg per day, 81 to 105 kg = 1200 mg per day, >105 kg = 1400 mg per day) administered in 2 divided doses with food. For patients with CrCl ≤50 mL per minute, including patients receiving hemodialysis, refer to the RBV tablet prescribing information for the correct RBV dosage.
4. The optimal Zepatier-based treatment regimen and duration of therapy for PegIFN/RBV/PI-experienced GT1a-infected patients with 1 or more baseline NS5A RAVs at positions 28, 30, 31, and 93 has not been established.
5. Patients who have failed treatment with PegIFN + RBV + HCV NS3/4A protease inhibitor (PI): boceprevir, simeprevir, or telaprevir.

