# Proprietary Information of MD Anderson

Protocol # 2016-0251

Date: February 24, 2020

46

Each Zepatier tablet contains 50 mg elbasvir and 100 mg grazoprevir, is beige, oval-shaped, film-coated, debossed with “770” on one side and plain on the other. The tablets are packaged into a carton (NDC 0006-3074-02) containing two (2) 14-count child-resistant dose packs for a total of 28 tablets.

Store Zepatier in the original blister package until use to protect from moisture. Store Zepatier at 20°C to 25°C (68°F to 77°F); excursions permitted between 15°C to 30°C (between 59°F to 86°F) [see USP Controlled Room Temperature].

In subjects with CrCl greater than 50 mL per minute, RBV will be administered twice a day (BID) PO (in RBV containing arms) at a total daily dose of 800 mg to 1400 mg based on subject weight on Day 1 (Table 5). RBV will be used for 12 to 16 weeks.

Table 5 Recommended Dosing for RBV in Combination Therapy for Subjects with CrCl Greater Than 50 mL Per Minute.

Body Weight in kg (lbs)	RBV Dose	Ribavirin capsules
<66 (<144)	800 mg/day	2 × 200 mg capsules A.M. 2 × 200 mg capsules P.M.
66-80 (145-177)	1000 mg/day	2 × 200 mg capsules A.M. 3 × 200 mg capsules P.M.
81-105 (178-231)	1200/mg day	3 × 200 mg capsules A.M. 3 × 200 mg capsules P.M.
>105 (>231)	1400 mg day	3 × 200 mg capsules A.M. 4 × 200 mg capsules P.M.

Abbreviations: A.M. = ante meridian; P.M. = post meridian; RBV = ribavirin.

Trial Treatment should begin within 3 days of allocation/assignment. However, every effort should be made to begin trial treatment on the day of allocation (ie, Cycle 1 Day 1).

The investigator shall take responsibility for and shall take all steps to maintain appropriate records and ensure appropriate supply, storage, handling, distribution and usage of trial treatments in accordance with the protocol and any applicable laws and regulations.

All trial treatments will be administered on an out-patient basis.

All products indicated in Table 3 will be provided centrally by Merck or locally by the trial site, subsidiary or designee, depending on local country operational or regulatory requirements.

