# Proprietary Information of MD Anderson

Protocol # 2016-0251

Date: February 24, 2020

63

hemoglobin may be significant, it is advised that hemoglobin or hematocrit be obtained before the start of treatment and at Week 2 and Week 4 of therapy, or more frequently if clinically indicated. Subjects should then be followed as clinically appropriate. Fatal and nonfatal myocardial infarctions have been reported in patients with anemia caused by RBV. Subjects should be assessed for underlying cardiac disease before initiation of RBV therapy. Subjects with pre-existing cardiac disease should have electrocardiograms (ECGs) administered before treatment, and should be appropriately monitored during therapy. If there is any deterioration of cardiovascular status, therapy should be suspended or discontinued. Because cardiac disease may be worsened by drug-induced anemia, patients with a history of significant or unstable cardiac disease should not use RBV.

RBV should not be used in subjects with CrCl less than 50 mL/min. Subjects with impaired renal function and those over the age of 50 should be carefully monitored with respect to development of anemia.

If severe AEs or laboratory abnormalities develop during the study, RBV can be modified based on the recommended guidelines provided in Table 8.

For subjects with a history of stable cardiovascular disease, a permanent dose reduction is required if the hemoglobin decreases by greater than or equal to 2 g/dL during any 4-week period. In addition, for these cardiac history patients, if the hemoglobin remains less than 12 g/dL after 4 weeks on a reduced dose, the patient should discontinue combination therapy. It is recommended that a patient whose hemoglobin level falls below 10 g/dL have his/her RBV dose modified or discontinued per Table 9.

Subjects exhibiting the following conditions should be closely monitored and may require dose reduction or discontinuation of RBV therapy. Refer to the prescribing information:

- Hemolytic anemia may occur with a significant initial drop in hemoglobin
- Pancreatitis
- Pulmonary infiltrates or pulmonary function impairment
- New or worsening ophthalmologic disorders
- Concomitant administration of azathioprine
- Severe decreases in neutrophil and platelet counts and hematologic, endocrine and hepatic abnormalities
- Dental/periodontal disorders with combination therapy

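### The creatinine clearance limit for ribavirin is applied at entry to only one of the Arm B groups assigned ribavirin, and the dosing instructions below 50 mL/min conflict

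*Combined protocol and SAP*

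**What the plan says.** **Entry.** Exclusion 31 (Section 5.1.3) is the only numeric renal limit tied to ribavirin: "For Arm B subjects with HCV GT1a and have resistance polymorphisms are excluded if they have a CrCl of less than 50 mL/min". Everyone else is governed by Table 2 (inclusion 19). It accepts creatinine up to 1.5 x ULN with no clearance floor, or clearance of at least 30 mL/min when creatinine is higher.

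**Assignment.** Table 4 (Section 5.2) gives Zepatier plus ribavirin to the GT1a polymorphism group. It gives the same combination to the row for GT1a or "GT1b: PegIFN/RBV/PI-experienced" subjects (12 weeks) and to "GT4: PegIFN/RBV-experienced" subjects (16 weeks).

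**Dosing at low clearance.** Four places speak to this:
- Section 5.2.1.5: "RBV should not be used in subjects with CrCl less than 50 mL/min".
- Section 5.2, text before Table 5: "In subjects with CrCl greater than 50 mL per minute, RBV will be administered twice a day". No dose is given at or below 50.
- Table 4 footnote 3, for clearance at or below 50: "refer to the RBV tablet prescribing information for the correct RBV dosage".
- Section 4.3.3.3: "For patients with CrCl less than or equal to 50 mL per minute, including patients receiving hemodialysis, refer to the RBV tablet".

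**The concern.** A renal safety limit for a drug should apply to everyone assigned that drug. Here it follows one genotype subgroup. The other ribavirin groups can be eligible at a clearance where one section withholds the drug and two others point to an outside label.

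If Section 5.2.1.5 governs, the subject has no usable row in Table 4, because each uncovered row lists only the ribavirin-containing regimen. Once any study treatment is given, that subject counts in the ASaT population for SVR12 (Section 8.13.2) and is not replaced (Section 5.7).

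If footnote 3 governs, the subject receives ribavirin at a renal function where Section 5.2.1.5 advises against it. That section also explains the danger: "Fatal and nonfatal myocardial infarctions have been reported in patients with anemia caused by RBV". It asks for careful anaemia monitoring when renal function is impaired.

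**Working it through.** The plan states no figure on this point, so the check is mainly a cross-reading, with arithmetic to size it.

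**1. Which ribavirin groups does exclusion 31 miss?**

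| Table 4 group given ribavirin | Caught by exclusion 31? |
|---|---|
| GT1a with baseline NS5A polymorphisms | Yes |
| GT1a, PegIFN/RBV/PI-experienced, with polymorphisms | Yes |
| GT1a, PegIFN/RBV/PI-experienced, without polymorphisms | No |
| GT1b, PegIFN/RBV/PI-experienced | No |
| GT4, PegIFN/RBV-experienced | No |

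This reads the second row of Table 4 as the GT1a polymorphism group. The row as printed joins its conditions with an or; taken literally, it would only add further uncovered GT1a subjects.

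**2. Can the missed groups enrol?** Yes. Inclusion 13 admits subjects already treated for HCV. Exclusion 28 bars only prior regimens containing an NS5A inhibitor, so failure of PegIFN/RBV, with or without a protease inhibitor, is allowed.

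**3. Can they enrol below 50 mL/min?** Yes, by either route in Table 2. The clearance route explicitly allows 30 to below 50. The creatinine route sets no clearance floor. To illustrate that route, assume Cockcroft-Gault (the protocol names no formula): clearance = (140 − age) × weight / (72 × creatinine), × 0.85 for women.
- Man aged 65, 75 kg: clearance is 50 at creatinine 75 × 75 / (72 × 50) = 1.56 mg/dL. With an assumed ULN of 1.1, 1.2 or 1.3 mg/dL, that is 1.42, 1.30 or 1.20 × ULN, within the 1.5 × ULN limit in each case.
- Age 75, 55 kg, creatinine 1.0 mg/dL: 65 × 55 / 72 = 49.7 mL/min for a man; × 0.85 = 42.2 for a woman.

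**4. What happens next?** Take a GT4 PegIFN/RBV-experienced subject with clearance 40. Table 2 can admit the subject and exclusion 31 does not apply. Table 4 assigns ribavirin, Section 5.2.1.5 says not to use it, footnote 3 refers to a label for the dose, and Table 5 does not cover the case. Section 5.5.3 says ribavirin contraindications apply but gives no clearance value.

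The cut-points also disagree at exactly 50: exclusion 31 and Section 5.2.1.5 use below 50, while footnote 3 and Section 4.3.3.3 use at or below 50.

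**5. How many subjects?** The documents do not give the share both in a missed group and below 50. For GT4, the placebo-controlled phase III trial in Section 4.2.1.4 had 157 GT1a, 131 GT1b and 18 GT4 patients: 18 / 306 = 5.9%. If Arm B had that mix (an assumption), 15 × 0.0588 = 0.9 would be GT4, before requiring both PegIFN/RBV failure and clearance below 50. No share is given for protease-inhibitor-experienced subjects.

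**6. Effect on SVR12 if one subject goes without ribavirin.** From the treatment-experienced phase III trial in Section 4.2.1.4:
- 12 weeks: 98/104 − 97/105 = 1.8 points; 1.8 / 15 = 0.12 points on the arm rate.
- 16 weeks: 103/106 − 97/105 = 4.8 points; 4.8 / 15 = 0.32 points.

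No ribavirin-free comparison is shown for protease-inhibitor-experienced patients, so these differences may not carry over to them.

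**The case against.** The strongest reply is that the protocol's operative text points one way. Section 5.2.1.5 has no exception, and Table 5 doses only above 50. The referrals to the label look carried over from elsewhere: they cite the tablet label although the trial supplies capsules (Tables 3 and 19), and they provide for haemodialysis although exclusion 19 names dialysis as an investigator-judged ground for exclusion. What that label says is not in the documents.

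There are also safeguards. Exclusion 30 removes significant or unstable cardiac disease before dosing and also lists proven coronary disease or angina. Entry requires haemoglobin of at least 9 g/dL. Haemoglobin is checked at Weeks 2 and 4, and Table 8 sets reduction and stopping rules. Exclusions 19 and 33 let the investigator refuse an unsuitable candidate. Finally, the affected group may be empty: Section 4.2.1.3 places the boceprevir and telaprevir regimens in 2011 to 2013.

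Most of this stands as a reason to rate the risk low. It does not close the gap. If Section 5.2.1.5 is taken to govern, the eligible subject still has no listed regimen. Discretion is only a partial safeguard, and the protocol did not rely on it elsewhere: exclusion 30 applies its cardiac limit at entry whatever the genotype, and exclusion 31 sets a number for one ribavirin group without saying why the others differ. Haemoglobin monitoring acts only after exposure has begun.

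**Conclusion.** The concern holds. Exclusion 31 is narrower than the set of Arm B regimens containing ribavirin, and the instructions for the missed subjects contradict one another below 50 mL/min. This follows from the text alone.

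The size is small: probably zero or one of about 15 Arm B subjects. That is a judgement, since the documents do not give the joint share; the clearance examples show that low values can pass Table 2, and say nothing about how often. For one affected subject, the expected SVR12 rate shifts by about 0.1 to 0.3 points, assuming the treatment-experienced trial's differences apply. The case for change rests on subject safety and on having a usable regimen for everyone admitted.

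**What to change.** - Reword exclusion 31 to exclude any Arm B subject whose Table 4 regimen includes ribavirin and whose clearance is below the limit in Section 5.2.1.5.
- Delete the label referrals in Table 4 footnote 3 and Section 4.3.3.3, or align them with Section 5.2.1.5.
- Use one cut-point in exclusion 31, Section 5.2.1.5, footnote 3, Section 4.3.3.3 and Table 5. Ribavirin only above 50 mL/min would match the existing dosing table; it requires a small change to exclusion 31 and Section 5.2.1.5, which currently leave a value of exactly 50 permitted.

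The cost is a wording amendment and very few lost candidates, probably zero or one.
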